7.1.8. Safety Analysis

The analysis of primary safety endpoints will include assessments of AEs, vital signs, 12-lead ECGs, infusion-site observations, physical examination, hepatic ultrasound results, and clinical laboratory evaluations including glucose values. All safety analyses will be performed using the Safety Population.

Adverse Events:

Adverse Events will be coded using (MedDRA version 25.0 Mar 2022) AE coding system for the purpose of summary tables. Treatment-emergent adverse events (TEAE) will be summarized by cohorts and RZ358 Total and AEs that are non-TEAE will be identified.

For each cohort, AEs will be summarized with frequency count and percentage by MedDRA SOC and PT, with all patients treated in that cohort as the denominator, unless otherwise specified. In addition, AEs will also be summarized by severity and relationship to study drug.

All AEs and TEAEs during the study will be summarized for the respective cohorts. A patient experiencing the same AEs and TEAEs multiple times will be counted only once for that PT. Similarly, if a patient experiences multiple AEs and TEAEs (preferred terms) within the same SOC then that patient will be counted only once for that SOC. When summarizing by severity, the event with highest severity will be counted. All AEs will be listed in chronological order of the events occurred.

For purposes of this study, TEAEs for summary tabulation will be further defined as those events which occur within a period of time through the +42 days follow-up visit after the final dose of study drug. Adverse events with onset after ICF but before first dose of study drug or after last dose of study drug +42 days will be identified separately from TEAEs.

Summary tables of the following AEs will be provided:

An overview of TEAE summary will be presented by cohorts, and it will include:

- Number of Subjects with any TEAEs
- Number of subjects with any TEAEs related to study drug
- Number of subjects with any TEAEs leading to treatment/study discontinuation
- Number of subjects with TEAEs by maximum severity grade
- Number of Subjects with any serious TEAEs
- Number of Subjects with any serious TEAEs related to study drug
- Number of Subjects with any serious TEAEs leading to treatment/study discontinuation
- Number of Subjects with any serious TEAEs leading to death

➤ Number of subjects with any non-TEAEs

A summary of the frequency (number and percentage of patients) of TEAEs and serious TEAEs by cohort will be presented by SOC, PT, and non-TEAEs will be separately identified.

Similarly, summary results will be generated for TEAEs by SOC, PT for severity grade ≥ 3 .

A summary of the frequency (number and percentage of patients) of TEAEs by cohort will be presented by SOC, PT and by related to study drug.

A summary of the frequency (number and percentage of patients) of TEAEs leading to treatment/study discontinuation by cohort will be presented by SOC and PT.

All AEs reported during the study will be present in a by-patient listing. Separate by-patient listings will be generated to present AEs, SAEs leading to discontinuation from treatment and the study and TEAEs leading to death.

Infusion Site Reactions:

A local infusion site reaction is any local reaction occurring at the site of injection following study drug administration. A local infusion site reaction, including, but not limited to, erythema, induration, and pain, should be reported as an adverse event.

Infusion site reactions will be summarized by cohort and RZ358 Total using frequency count and percentage for safety population.

All infusion site reactions will be presented in listing for safety population.

(b) (4)

(b) (4)

Vital signs:

Vital signs measurement will include systolic and diastolic blood pressure (mmHg), temperature (degree Celsius), pulse rate (beats/minute) and respiratory rate (breaths/minute).

The actual and change from baseline values at each scheduled time-point will be summarized by visit, cohort and RZ358 Total (pediatric and adult patients) using descriptive statistics (n, Mean, SD, Median, Minimum, and Maximum) for Safety population. For categorical shift summaries, any available pre-treatment values (screening or pre-treatment baseline) may be used to define baseline, for the categorical assignment.

All vital signs data will be presented in listings for Safety population.

The below table will be referred to for the vital signs abnormalities.

Table 2: Vitals Abnormality

VS Ranges	1-3 Years	4-5 Years	6-8 Years	9-12 Years	13-16 Years	17-Onwards	≤12	≥13	Min	Max
Systolic BP							80-120	90-140		
Diastolic BP							50-80	55-90		
Temperature									36.0	38.0
Respiratory Rate							18-30	12-20		
Pulse Rate	94-179	72-195	61-116	54-111	47-108	60-100				

12-Lead ECG:

The 12-lead ECG measurements will include heart rate (bpm), QRS (msec), QT (msec), corrected QT (msec), RR (msec), and PR (msec) intervals, as well as an overall interpretation.

Actual and change from baseline value of quantitative ECG parameters will be summarized using descriptive statistics (n, Mean, SD, Median, Minimum, and Maximum) by visit, cohort and RZ358 Total (pediatric and adult patients) for safety population.

Overall assessment of safety ECGs (Normal, Abnormal - NCS, Abnormal – CS) will be summarized using frequency counts and percentage by visit, cohort and RZ358 Total for safety population. In addition, a shift table comparing overall interpretation (Normal, Abnormal - NCS, Abnormal - CS) of the ECG parameters at baseline vs treatment-emergent post-baseline (worst treatment-emergent category) will also be presented by cohort for safety population. For categorical shift summaries, any available pre-treatment values (screening or pre-treatment baseline) may be used to define baseline, for the categorical assignment.

Individual data listings of ECG results along with the Investigator-identified ECG abnormalities will be presented for each patient.

Clinical Laboratory Data

The Clinical Laboratory test category will include assessments of Hematology, Chemistry, Urinalysis, HbA1c, ADA Blood Collection.

(b) (4)

Quantitative parameters of hematology, chemistry, and urinalysis, actual and change from baseline values at each scheduled time-point will be summarized by visit, cohort and RZ358 Total (pediatric and adult patients) using descriptive statistics (n, Mean, SD, Median, Minimum, and Maximum) for safety population. All qualitative result parameters at each scheduled time-point will be summarized by visit, cohort and RZ358 Total using frequency counts and percentage for safety population.

Additionally, comparing the changes in categorical laboratory variables from baseline (Low, Normal, and High) / (Positive, Negative) vs treatment-emergent post-baseline (worst treatment-emergent category) will be presented by cohort using a shift table for safety population. For categorical shift summaries, any available pre-treatment values (screening or pre-treatment baseline) may be used to define baseline, for the categorical assignment.

A summary table will be presented for HbA1c by visit, cohort and RZ358 Total for safety population.

Anti-drug Antibody (ADA): Anti-drug Antibody (ADA) with categories ADA Negative, Pre-existing Immunoreactivity, Treatment Boosted, and Treatment-emergent. Positive will be summarized by cohort, and RZ358 Total using frequency count and percentage for safety population.

Definitions:

ADA Negative: defined as negative response in the ADA assay at all time points and those that exhibit a pre-existing response, regardless of any missing samples.

Pre-existing Immunoreactivity: defined as either a positive response in the ADA assay at baseline with all post first dose ADA results negative OR a positive response at baseline with all post dose ADA response less than 4-fold of baseline titer levels.

Treatment Boosted ADA: defined as a positive response post first dose that is greater than or equal to 4-fold over baseline titer level, when baseline results are positive.

Treatment-emergent Positive (D): defined as an ADA positive response post first dose when baseline results are negative or missing, OR ADA positive response more than 4-fold of a positive baseline titer.

Additionally, comparing the changes in categorical ADA Blood Collection from baseline (Positive, Negative) to post baseline visit will be presented by cohort using a shift table for safety population.

Individual data listings of laboratory results will be presented for hematology, chemistry, urinalysis HbA1c and ADA Blood Collection separately.

Physical examination:

The investigator or qualified designee will perform a complete physical examination (genitourinary examination not required) and targeted abbreviated physical examinations.

A full physical examination will include, at a minimum, assessment of the following systems: skin, head, ears, eyes, nose and throat, respiratory system, cardiovascular system, gastrointestinal system, neurological condition, blood and lymphatic systems, and the musculoskeletal system. An abbreviated physical examination is inclusive of neurological, cardiac, gastrointestinal, and pulmonary assessments.

The physical examination findings (Normal, Abnormal NCS, Abnormal CS) will be summarized using counts and percentages by visit, cohort and RZ358 Total for each body system using safety population.

Additionally, for each body system, changes in physical examination findings from baseline vs treatment-emergent post-baseline (worst treatment-emergent category) will be presented using a shift table for each cohort using safety population. For categorical shift summaries, any available pre-treatment values (screening or pre-treatment baseline) may be used to define baseline, for the categorical assignment.

All physical examination findings will also be presented in listing for safety population.

Hepatic Ultrasound

Hepatic ultrasound will be performed at the specified time points as listed in the Schedule of Assessments, and per the Investigator's institution's standard practice methodology. The results will be interpreted by qualified personnel.

The overall interpretation of hepatic ultrasound (Normal, Abnormal NCS, Abnormal CS) will be summarized using counts and percentages by visit, cohort and RZ358 Total for safety population.

Additionally, changes in overall interpretation of hepatic ultrasound from baseline vs treatment-emergent post-baseline (worst treatment-emergent category) will be presented using a shift table for each cohort using safety population. All hepatic ultrasound results will also be presented in listing for safety population.

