4.3 Inclusion Criteria

Patients who meet ALL of the following criteria are eligible to participate in the study.

1. Provide written informed consent and, as applicable, assent, before any study-specific procedures are performed.
2. At Screening, aged ≥ 12 years and ≤ 45 years.
3. An established clinical diagnosis, with or without a genetic diagnosis, of congenital hyperinsulinism.
4. Patient is currently receiving SOC medications (e.g., diazoxide, lanreotide, sirolimus, pasireotide, or octreotide) and/or nutritional supplementation for CHI, with at least 2 months of stable treatment; OR is not on treatment at the time of Screening.
5. Glucose values <70 mg/dL (3.9 mmol/L) for $\geq 4\%$ of the overall monitored CGM time with at least 3 severe hypoglycemia events by CGM threshold of <50 mg/dL (2.8 mmol/L) during the last 7 days of a 10-day Screening CGM evaluation period.

(b) (4)

AND:

Experiencing ≥ 3 hypoglycemia events (<70 mg/dL) per week by SMBG and/or according to the Investigator's evaluation.

6. Hepatic ultrasound at Screening without clinically significant findings, including clinically significant gallstones as judged by the Investigator (e.g. large size, obstructive, biliary colic or LFT abnormalities exceeding protocol thresholds), or evidence of peliosis hepatitis.

7. For female patients of childbearing potential, a negative serum or urine pregnancy test within 7 days before dosing;
 - Females of childbearing potential are defined as fertile following menarche and until becoming postmenopausal or permanently sterile. (Postmenopausal is defined as absence of vaginal bleeding or spotting for at least 1 year. Permanently sterile is defined as having had a hysterectomy, bilateral salpingectomy, or bilateral oophorectomy.)
 8. For female patients of childbearing potential, a willingness to use highly effective* contraceptive measures adequate to prevent a new pregnancy for the duration of the study, including for at least 105 days after receiving the last dose of study drug. For women with reproductive potential who use a hormonal method of contraception, concurrent use of a second (barrier) method is recommended.

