AUTHORIZATION: I, the undersigned, declare that I have reviewed the statistical analysis plan along with TLF mock-ups and that to the best of my knowledge the document accurately reflects the protocol objectives.

Authorized by:

(b) (4)

REVISION HISTORY

Version	Date	(b) (4)	Reasons
1.0	APR 20, 2022	(b) (4)	
1. Changes in versions, MedDRA-25.0 and WHODD- WHODRUG B3 SEP2019.2. Anticipated list of TLFs has been updated.3. Added the two new listings for derived endpoint variables (CGM and SMBG).4. Updated the section “Subgroup Analysis (7.1.11.)” due to the addition of one subgroup (Patients ages 2-6 years old) for two endpoints.5. Updated the section “Safety Analysis (7.1.8.)” by adding a table of Vitals Abnormality.6. Updated the section “Analysis Population (6.1)” with the modification of Per Protocol Population definition.7. Updated the section “Efficacy Analysis” with addition of percent change summary and analysis for two efficacy endpoints.

LIST OF ABBREVIATIONS

Abbreviation or special term	Explanation
ADA	Anti-drug antibody
AE	Adverse event
ALT	Alanine aminotransferase
AM	Ante Meridiem
AOC	Area over the curve
AST	Aspartate aminotransferase
AUC	Area under the curve
CGM	Continuous glucose monitoring
CHI	Congenital hyperinsulinism
cm	Centimeters
CS	Clinically significant
CV	Coefficient of variation
DERC	Dose Escalation Review Committee
dL	Deciliter
ECG	Electrocardiogram
eCRF	Case report form
FFA	Free fatty acids
HbA1c	Hemoglobin A1c
Kg	Kilograms

Abbreviation or special term	Explanation
MedDRA	Medical Dictionary for Regulatory Activities
mg	Milligram
mL	Milliliter
msec	Millisecond
NCS	Not clinically significant
PD	Pharmacodynamics
PK	Pharmacokinetics
TLF	Table, Listing and Figure
PM	Post Meridiem
POC	Point of care
RTSM	Randomization and Trail Supply Management
SAE	Serious adverse event
SD	Standard deviation
SE	Standard Error
SoC	Standard of care
SOC	System Organ Class
SMBG	Self-Monitoring of Blood Glucose
TEAE	Treatment emergent adverse event

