2.2. Study Design

This is a Phase 2, multi-center, open-label, multiple ascending dose study to evaluate the safety, tolerability, PK, PD, and glycemic efficacy of RZ358 in patients with hypoglycemia due to CHI. The

study will consist of up to 4 dose cohorts, which are to be enrolled independently and conducted sequentially, comprised of up to 6-8 patients per cohort to ensure each cohort includes at least 3 patients aged \leq 10 years. Eligible patients will be successively enrolled into the cohort that is open for enrollment at that time, at the lowest dosing cohort that is yet to be filled.

In Cohorts 1, 2, and 3 the dose amount will be fixed during the entire 8-week Treatment Period, while in Cohort 4 there will be a scheduled bi-weekly dose-titration for the first 4 weeks, followed by a fixed dose amount thereafter for the remaining 4 weeks. The Sponsor may decide to add a cohort to repeat a dose level or to study an additional dose level, but the dose level for any cohort will not exceed the planned dose level for that cohort, as specified in this protocol.

Advancement to subsequent cohorts will not occur until at least 4 patients from the prior cohort have each received at least 4 weeks of study drug (2 bi-weekly doses), without safety concerns. A Dose Escalation Review Committee will assess all available and relevant interim data from each cohort to determine the appropriateness of dose escalation to a new cohort.

Table 1: Study Design/Cohort Dosing Regimens

Cohort	Dosing (mg/kg)			
	Wk 1	Wk 3	Wk 5	Wk 7
1	3	3	3	3
2	6	6	6	6
3	9	9	9	9
4	3	6	9	9

Following informed consent, patients will complete a Screening Period to determine eligibility. After the preliminary screening assessment, patients who are otherwise eligible will undergo scheduled self-monitoring of blood glucose (SMBG) by point of care (POC) glucometer as well as have a CGM sensor placed according to the instruction manual, for completion of a minimum 10-day outpatient CGM evaluation to assess glycemic eligibility and establish a baseline. (b) (4)

patients will use an SMBG for their POC throughout the trial. Patients taking existing and stable doses of standard of care (SoC) medications or nutritional supplementation for CHI at the time of screening should continue the same regimen and doses throughout this period.

(b) (4)

(b) (4)

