7.1.2. Demography and Baseline Characteristics

The demographic and baseline characteristics will include age (years), age group (2-6, 7-11, 12-17 and ≥ 18 years), gender, ethnicity, race, height (cm), weight (kg), and BMI (kg/m^2). These will be summarized by cohort and RZ358 Total, for the ITT Population and Per protocol (PP) Population.

Baseline CHI characteristics will include genetic type, CHI medication history, pancreatectomy, exocrine pancreatic insufficiency, repeat surgeries, tube feeding catheter, and type of nutrition and will be summarized by cohort and RZ358 Total, for ITT Population.

Descriptive statistics (n, mean, SD, minimum, median, and maximum) will be presented for continuous variables. Count and percentage will be presented for each class of the categorical variables.

All individual patient demographic and baseline characteristic data will be listed.

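### In the SAP's vital-sign abnormality table, the upper pulse limit of 195 for ages 4-5 is out of order with both neighbouring age bands and should be verified before the output is programmed

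*SAP*

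**What the plan says.** SAP 7.1.8, under vital signs, introduces Table 2 with the sentence "The below table will be referred to for the vital signs abnormalities". The column heads are "VS Ranges 1-3 Years 4-5 Years 6-8 Years 9-12 Years 13-16 Years 17-Onwards", followed by further columns used for blood pressure, temperature and respiratory rate. The pulse row is "Pulse Rate 94-179 72-195 61-116 54-111 47-108 60-100". The unit comes from the same section: "pulse rate (beats/minute) and respiratory rate (breaths/minute".

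The table is current text. The SAP revision history records that the safety section was updated "by adding a table of Vitals Abnormality". No source is cited for the limits, and nothing explains the 4-5 year entry.

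On who could fall in that band, SAP 7.1.2 tabulates "age group (2-6, 7-11, 12-17 and ≥ 18 years", and SAP 2.2 sizes the cohorts "to ensure each cohort includes at least 3 patients aged" 10 or under. The supplied protocol, in section 4.3, admits only patients "At Screening, aged ≥ 12 years and ≤ 45 years". The SAP introduction names two versions of protocol amendment 5.0, one of them a US version.

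**The concern.** Table 2 is the rule by which a recorded pulse is called normal or abnormal. Repeat-dose safety and tolerability is a primary endpoint (SAP 5.1), and vital signs are among its assessments. Five of the six upper limits fall steadily with age. The 4-5 year entry instead lies above the limit for younger children and far above the limit for the next older band. If 195 is a slip, a programmer who follows the table will count as normal some pulses in 4-5 year olds that the same table calls abnormal in both adjacent bands. The descriptive summaries are by visit and cohort and do not separate narrow age bands. Among the vital-sign outputs described, Table 2 is therefore the one that judges pulse against age. With 6-8 patients per cohort, one misclassified child changes a reported count.

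**Working it through.** No test, power or sample-size figure is involved. The check compares adjacent cells of the pulse row in SAP Table 2, in beats/minute. The row has six ranges for six age bands, so a shifted column does not explain the value.

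| Age band (years) | Lower | Upper | Change in upper from previous band | Width (upper minus lower) |
|---|---|---|---|---|
| 1-3 | 94 | 179 | n/a | 179 - 94 = 85 |
| 4-5 | 72 | 195 | 195 - 179 = +16 | 195 - 72 = 123 |
| 6-8 | 61 | 116 | 116 - 195 = -79 | 116 - 61 = 55 |
| 9-12 | 54 | 111 | 111 - 116 = -5 | 111 - 54 = 57 |
| 13-16 | 47 | 108 | 108 - 111 = -3 | 108 - 47 = 61 |
| 17 onwards | 60 | 100 | 100 - 108 = -8 | 100 - 60 = 40 |

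1. **Upper limits.** The only rise is at 4-5 years (+16). The step down to 6-8 years is 79, against later steps of 5, 3 and 8.
2. **Lower limit of the same band.** The sequence 94, 72, 61 is in order, so the anomaly is confined to one cell.
3. **Width.** The 4-5 year range is the widest in the row, 123 / 55 = 2.2 times the 6-8 year range.
4. **Contradiction inside the table.** A pulse of 185 is above 179 (abnormal at 1-3), below 195 (normal at 4-5) and above 116 (abnormal at 6-8). The same holds for every value from 180 to 195.
5. **Range if the limit was meant to fall with age (an assumption).** The intended upper limit U would then lie between 116 and 179, and the whole-number pulses wrongly counted as normal would run from U + 1 to 195, which is 195 - U values.
   - U = 179: 180-195, or 195 - 179 = 16 values.
   - U = 116: 117-195, or 195 - 116 = 79 values.

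   Under this assumption 180-195 is affected whatever U is; 117-179 is affected only in part or not at all, depending on U.

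**The case against.** The strongest reply is that the SAP never says the limits must fall with age, so 195 is unusual rather than impossible. That stands as far as it goes: the documents do not prove a typing error. They do show a table that treats 180-195 as abnormal on both sides of the 4-5 year band and normal within it, without explanation.

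The size of the 79-beat step is also open to challenge. The table already falls by 179 - 116 = 63 between ages 1-3 and 6-8, so a large drop around this age exists whatever the 4-5 year value is. This too stands, and the rise of 16 is the firmer evidence.

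The practical reach is limited as well. SAP 7.1.8 lists all vital signs by patient and summarizes them with minimum and maximum. It reports ECG heart rate with an overall normal/abnormal interpretation, and adverse events are collected independently of Table 2. No visible text ties Table 2 to dosing or stopping. The supplied protocol enrols no one under 12, and a minimum of 3 patients aged 10 or under per cohort does not guarantee any aged 4-5. All of this limits the consequence but does not remove the inconsistency.

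A reader might also infer that the lower limit of 60 at 17 onwards is wrong, because it rises from 47 at 13-16 and a pulse of 50 changes status between 16 and 17. The documents do not support that. Steps at band edges occur elsewhere in the same table: a systolic pressure of 85 is within 80-120 at age 12 but outside 90-140 at 13, and a respiratory rate of 25 is within 18-30 at 12 but outside 12-20 at 13.

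**Conclusion.** The 4-5 year upper pulse limit is inconsistent with the rest of its row and needs verification. The demonstrated size is the interval 180-195, which is abnormal at 1-3 and 6-8 years but normal at 4-5. Two stronger readings are tempting:

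- **That fast pulses in the youngest patients are never flagged.** The table flags ages 1-3 above 179 and ages 4-5 above 195.
- **That all of 117-195 is misclassified at 4-5 years.** This needs an intended limit of 116, and the documents give no intended limit.

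The effect is confined to the abnormality flag, and any shift category built on it, for patients aged 4-5. The conclusion rests on two assumptions. The first is that 195 is what the SAP page prints, which the check against source would settle. The second is that 4-5 year olds are enrolled. The SAP's 2-6 year group points to that, presumably through a protocol version other than the one supplied.

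**What to change.** Before programming the abnormality output, check the 4-5 year pulse range in Table 2 against the source from which it was taken. Then either correct the upper limit or state in the SAP why it exceeds the limit for younger children. Produce the output with the verified limit, or re-run it if it already exists. No replacement value is proposed here, because the documents do not contain one. The cost is one table cell or one sentence in the SAP, and at most one re-run output. No data collection or other analysis changes.
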